EFFECTS OF AN ELASTIC BANDAGE PROTOCOL IN INDIVIDUALS WITH CHRONIC ANKLE INSTABILITY

NCT number: unavailable

Date of document: May 22, 2020

Procedures: The volunteers will complete the sample characterization form containing the demographic data (age, sex, weight, height, BMI, dominance, level of physical activity, history of injuries in the lower limbs) and will sign the informed consent form. Then, they will answer the Cumberland Ankle Instability Tool questionnaire - brazilian-portuguese version and the American Orthopedic Foot and Ankle Society - Ankle-hindfoot Scale validated for Portuguese.

After characterization of the sample and randomization in certain groups, evaluations of static postural control will be carried out through the force platform (BIOMECH400, EMG System do Brasil, SP Ltda.) In unipodal support on the unstable ankle. In the assessment of postural control, participants will be instructed to remain in unipodal support, barefoot for thirty seconds looking at the horizon (a mark will be fixed on the wall at a height of 2 meters), with the upper limbs relaxed beside the body, free lower limb without touching the test limb, maintaining knee flexion position at 90°. Participants will perform the test three times with a 30-second rest interval between each run.

Subsequently, the Y Balance Test will be performed, which consists of reaching the greatest possible distance in three different directions (anterior, posterolateral and posteromedial) with the limb contralateral to the unstable ankle while this limb remains supported in the center of the intersection of measuring tapes in Y shape. (47) Each of the directions is tested three times and the 3 repetitions are averaged.

Finally, the side hop test will be performed, which consists of one-legged lateral jumps over a distance of 30 cm between markings on the ground. There will be 10 jumps, which will be counted from the starting point until the return to it. Participants will be instructed to perform as quickly as possible. In the event of a fall, touch of the pending limb to the ground or failure to pass the mark, the test will be discarded and performed again.

Performed the three postural control tests, an elastic bandage will be applied on the ankle with instability or on the ankle with the lowest score on the CAIT questionnaire (in case of bilateral instability), if there is bilateral instability with the same score on the CAIT-p, bandaging will be performed in the dominant lower limb. The application area will be previously free of hair (performing trichotomy) and asepsis with 70% alcohol. The technique used will be the “technique for stabilizing the ankle”, where an “I” tape without a fixed point is placed from one malleolus to the other by the hindfoot and another “I” tape without a fixed point involves the ankle joint, starting from the calcaneal tendon to cross in front of the talus. The application will be carried out by a professional qualified by the Therapy Taping Method®.

After applying the bandage, the volunteers will again perform the tests mentioned above. They will be instructed on how to care for the bandage (do not dry the area by rubbing the towel, but with light touches, do not cut the ends of the bandage if they are peeling off, do not remove and replace the bandage) to preserve the application and keep the application up to the room day after placed.

- Experimental group: the application of the bandage will be carried out weekly, for five weeks, in the individuals allocated to this group. Each week the tension of the tapes will be increased, increasing 5% of tension per week in relation to the initial length.

- Control Group: the application of the bandage will be carried out weekly, for five weeks, in the individuals allocated to this group. The applications will not suffer an increase in the tension of the tapes, they will only be placed on the application site.

Initial assessment will be carried out on the first day, reevaluations in the third week and in the sixth week after the initial assessment.

- Data analysis:

The normal distribution of the sample data will be analyzed using the Shapiro Wilk test. If normality is established, an analysis of variance of the factors will be used for each dependent variable to compare the groups (elastic bandage without tension and elastic bandage with tension) in both tasks. All statistical analyzes will be performed in the SPSS statistical program (version 20.0) with the adopted significance of 5% ($p < 0.05$).

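### Randomisation comes before the pre-tape performance tests although the allocation is not needed until taping, an avoidable risk mainly to the Y Balance and side hop baselines

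*Combined protocol and SAP*

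**What the plan says.** All of this is in the combined protocol and SAP, under Procedures unless stated otherwise.

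- Characterisation comes first and includes the questionnaires: "Then, they will answer the Cumberland Ankle Instability Tool questionnaire", followed by the AOFAS scale.
- Randomisation and the force platform come next: "After characterization of the sample and randomization in certain groups, evaluations of static postural control will be carried out through the force platform".
- The Y Balance Test follows, which asks for "reaching the greatest possible distance in three different directions".
- The side hop test is last: "Participants will be instructed to perform as quickly as possible". Its repeat rule is: "In the event of a fall, touch of the pending limb to the ground or failure to pass the mark, the test will be discarded".
- Then comes the tape: "Performed the three postural control tests, an elastic bandage will be applied on the ankle with instability". The battery is repeated once the tape is on: "After applying the bandage, the volunteers will again perform the tests mentioned above".
- Both arms are taped weekly for five weeks. Tension rises each week in the experimental arm; for the control arm the text says "The applications will not suffer an increase in the tension of the tapes".
- Reassessments are set for weeks 3 and 6 after the first-day assessment. The Data analysis paragraph names an analysis of variance for each dependent variable to compare the groups. It does not say which factors enter or how the first-day values are used.

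The document describes no concealment and no masking. It does not say who runs the tests, or whether that person also applies the tape.

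**The concern.** A baseline recorded before allocation cannot be influenced by knowledge of the allocation. The written order gives up that protection and gains nothing in return, because the arm is not needed until the first tape.

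The exposed measurements are mainly Y Balance and side hop. Both depend on how hard the participant tries and how the tester encourages. In side hop someone also judges whether a run counts, although within three stated, observable criteria. The instrumented force platform stance is less exposed, and CAIT and AOFAS appear to be completed before randomisation.

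The group comparison is affected only if three things hold together:

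1. someone learns the allocation before the tests;
2. that knowledge shifts the baseline in one arm;
3. the analysis uses the pre-tape values.

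The document settles none of these. On the third, a first-day assessment with two reassessments makes a group-by-time, change-score or baseline-adjusted analysis plausible, and any of these would carry the shift into the treatment comparison. A larger sample would not remove it.

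**Working it through.** **Sequence.** The stated order is: form and consent, CAIT and AOFAS, randomisation, force platform, Y Balance, side hop, tape, repeat tests. Between randomisation and tape, the tests are described identically for everyone. The ankle to be taped is chosen by instability, then CAIT score, then dominance, and not by arm. Taping is therefore the first step that can use the allocation.

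**Size.** The plan gives no figure to reproduce, and every input below is an assumption.

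- p: share of one arm whose allocation is known before the tests (0 to 1)
- b: shift this causes in the baseline (0.1 to 0.3 SD)
- ρ: baseline to follow-up correlation (0.5 to 0.8), with unit variances
- k: number of occasions analysed, pre-tape included (3 for day 1, week 3 and week 6; 4 if the post-tape repeat is added)
- f: shift in every later test of the same arm, first taken as 0

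Size of the bias in SD, with f = 0:

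| Analysis | Formula | p = 0.25 | p = 1 |
|---|---|---|---|
| Change score, or baseline-to-follow-up group-by-time contrast | p × b | 0.025 to 0.075 | 0.10 to 0.30 |
| ANCOVA on baseline | ρ × p × b | 0.0125 to 0.06 | 0.05 to 0.24 |
| Group main effect, k = 3 | p × b / 3 | 0.008 to 0.025 | 0.033 to 0.10 |
| Group main effect, k = 4 | p × b / 4 | 0.006 to 0.019 | 0.025 to 0.075 |
| Follow-up values alone | none | 0 | 0 |

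For example, the ANCOVA limits are 0.5 × 0.25 × 0.1 = 0.0125 and 0.8 × 1 × 0.3 = 0.24. At p = 0 every entry is 0.

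**What reordering does if later tests also shift (p = 1).** The signed change-score bias goes from f − b to f. The group main effect goes from (b + (k − 1)f)/k to (k − 1)f/k.

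- b = 0.2, f = 0.05: the change-score bias falls in size from 0.15 to 0.05. The main effect falls from 0.100 to 0.033 (k = 3) or from 0.088 to 0.038 (k = 4).
- b = f = 0.2: the change-score bias rises from 0 to 0.20. The main effect falls from 0.20 to 0.133 (k = 3) or 0.15 (k = 4).

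Reordering alone therefore enlarges the change-score bias when 0 < b < 2f. If f = 0, reordering brings the bias to 0 in every analysis listed.

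**The case against.** The strongest reply is that the order of the draw is not itself an error. An allocation drawn early but kept sealed until taping does no harm, so what is missing is a statement on concealment. In so brief a document, silence is weak evidence that the safeguard is absent. Nothing shows that anyone knew the arm before testing. Both arms are taped and differ only in tension, so the motive to favour one is weaker than in a taped-versus-untaped trial. Y Balance averages three repetitions, and the side hop discard rule is observable. Finally, a tester who knows the arm on day 1 would probably know it later, so f = 0 is a generous assumption, and reordering alone can make a change score worse.

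Most of this stands as a limit on the claim: exposure is unproven, the size may be zero, and concealment until taping is as good as reordering. It does not remove the point. The plan does more than omit a detail: it states an order, and a safer one is available at almost no cost. The case where reordering worsens a change score is one where two biases happened to cancel. That is no reason to leave the baseline exposed, though it is a reason to protect the later tests too.

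**Conclusion.** The concern holds as an avoidable risk to the Y Balance and side hop baselines. The sequence and the absence of any described concealment or masking can be read directly from the document. The size cannot: it is unknown and may be zero. The illustrative ceiling of 0.30 SD requires that the whole of one arm is exposed, that the baseline shifts by 0.3 SD, that later tests do not shift, and that a change-score type of analysis is used. With a quarter of the arm exposed, the same analysis gives at most 0.075 SD. The change is worth making because it is cheap, not because harm has been shown. Confidence is medium.

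**What to change.** Complete and record the whole pre-tape battery first. Then randomise, or open an allocation concealed until that moment, immediately before the first tape, and disclose it only to the professional applying the tape. For the baseline these two options are equivalent. State in the protocol who holds the allocation, when it is released, and whether taper and tester are different people.

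This protects only the baseline. Where existing staff allow, also keep the allocation from whoever runs the post-tape, week-3 and week-6 tests. Masking the tester does not by itself exclude a shift that comes from the participant.

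The cost of the baseline part is small: someone must hold the allocation and release it between testing and taping, with no extra visit, measurement or staff. Masking the later tests needs a tester who is not the taper, and the document does not say whether that is already so.

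### The Y Balance analysis states no body-size scaling and no baseline or body-size covariate, so an unadjusted group comparison of reach would lose some precision

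*Combined protocol and SAP*

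**What the plan says.** In the combined protocol and SAP, the Procedures section describes the Y Balance Test as "reaching the greatest possible distance in three different directions (anterior, posterolateral and posteromedial", measured along tapes laid out in a Y. The only data reduction is "Each of the directions is tested three times and the 3 repetitions are averaged". No divisor, percentage or composite score follows.

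The characterization form in the same section records "age, sex, weight, height, BMI, dominance, level of physical activity, history of injuries in the lower limbs". Height is on that list and limb length is not.

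Under Data analysis, once normality is established, "an analysis of variance of the factors will be used for each dependent variable to compare the groups". The factors are not listed and no covariate is named. The paragraph does not name the Y Balance variable or its unit.

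On timing, the plan says "Initial assessment will be carried out on the first day, reevaluations in the third week and in the sixth week after the initial assessment". On day 1 the tests are done before the tape is applied and again afterwards, so there are two day-1 values that could be called baseline.

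**The concern.** How far a person reaches depends on leg length as well as on balance. Sex is recorded, and the text shows no restriction to one sex or to a height range, so body size will probably vary between participants. If the analysis compares mean reach between arms at a follow-up visit with nothing else in the model, that variation stays in the residual for all three directions. Confidence intervals are then wider and power lower than they need be, although the trial already collects data that would remove much of this variation.

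**Working it through.** The documents state no sample size, SD, effect size or power, so there is no figure of the plan's own to reproduce. All numerical inputs below are assumptions, shown as ranges.

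**1. Unadjusted group comparison.** Let R² be the share of between-person reach variance explained by the body-size covariate, assumed to be 10% to 30%. Adjustment multiplies the standard error by √(1 − R²), which is equivalent to a sample larger by 1/(1 − R²) − 1.

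| R² | SE multiplier | SE reduction | Equivalent extra sample |
|---|---|---|---|
| 0.10 | √0.90 = 0.949 | 5% | 11% |
| 0.20 | √0.80 = 0.894 | 11% | 25% |
| 0.30 | √0.70 = 0.837 | 16% | 43% |

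As an example, assume 20 per arm, a true difference of 0.6 SD and a two-sided 5% test (the plan does not state sidedness). Noncentral-t power is 0.456 unadjusted, and 0.496, 0.543 and 0.599 at R² = 0.10, 0.20 and 0.30.

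**2. Baseline reach also in the model.** Let ρ be the correlation between baseline and follow-up reach, assumed to be 0.6 to 0.9. With baseline alone the residual variance is 1 − ρ². With baseline and body size it is (1 − R²) − (ρ − R²)²/(1 − R²).

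- ρ = 0.9, R² = 0.1: 0.190 becomes 0.90 − 0.64/0.90 = 0.189, a further reduction of 0.6%.
- ρ = 0.6, R² = 0.3: 0.640 becomes 0.70 − 0.09/0.70 = 0.571, a further reduction of 10.7%.

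A second model gives a similar answer. Take raw reach as scaled reach times limb length, with assumed coefficients of variation (CV) of 6% to 12% for scaled reach and 5% to 8% for limb length, and a baseline-to-follow-up correlation of 0.7 to 0.9. By simulation, the baseline-adjusted variance on the raw scale is 1.01 to 1.12 times that on the scaled one. Together these give about 1% to 12%.

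**3. Change from baseline or group-by-time.** Adult limb length is essentially constant over six weeks. Under the multiplicative model, with mean change μ as a fraction of mean reach, the ratio of raw to scaled variance is (1 + CV_L²) + CV_L²μ²/[2·CV_R²(1 − ρ)], where L is limb length, R is scaled reach and ρ is now the correlation of scaled reach.

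- Smallest (CV_L 5%, μ = 0): 1.0025.
- Largest (CV_L 8%, CV_R 6%, ρ = 0.9, μ = 5%): 1.0064 + 0.000016/0.00072 = 1.029.

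The excess is therefore about 0% to 3%.

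**4. Dividing by limb length is not the same as adjusting for it.** To first order, the squared CV of reach divided by limb length is CV_Y²(1 − r²) + (r·CV_Y − CV_L)², where Y is raw reach and r² = R². With r² = 0.10 and illustrative CVs of 10% for reach and 6.5% for limb length, this is 100 × 0.90 + (3.16 − 6.5)² = 90 + 11.1 = 101.1, against 100 unscaled. The ratio then gains nothing. The gains in step 1 belong to covariate adjustment and carry over to the ratio only if reach is proportional to limb length.

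**The case against.** The strongest objection is that the analysis may already remove most of the problem. The plan speaks of factors in the plural and schedules assessments on day 1 and in weeks 3 and 6, so a group-by-time ANOVA is a natural reading. Body size then largely cancels from the interaction, though not from a group main effect. This stands as a limit on size: the 5% to 16% applies only to an unadjusted comparison. It does not remove the point, because group is the only comparison the plan names and neither a time factor nor a baseline term is written down.

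A second objection also stands. A reader might infer that the trial has decided to analyse raw distance. The documents do not say so. They describe how reach is collected and averaged, cite a reference for the test that is not available here, and are silent on scaling. Raw-scale analysis is an inference from that silence, although scaling by limb length could not be done from the data listed.

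A reader might also infer that an arm that is taller by chance would bias the result. With an assumed 20 per arm, the arms would differ by more than 0.3 SD in limb length in 2[1 − Φ(0.3/√(2/20))] = 34% of randomisations. But a 0.3 SD difference moves mean reach by only 0.3 × √R², or 0.09 to 0.16 SD for R² of 0.1 to 0.3. The standard error of the difference is √(2/20) = 0.316 SD, so the shift is about a third to a half of one standard error. Under randomisation that variation is already counted in the standard error and in the 5% error rate. It is the same precision loss seen from another side, not an additional harm.

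**Conclusion.** The point holds as a minor, conditional loss of precision in three directional outcomes. What the text supports is that no scaling is specified, limb length is not listed as measured, and no baseline or body-size covariate is named.

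Its size depends on the unstated model and on assumed variance shares. The full 5% to 16% applies only if the arms are compared on unadjusted reach, and little remains once each participant's own baseline is used. The 10% to 30% share is not a bound: the multiplicative model in the working, under its own assumed CVs, puts limb length at 15% to 64% of raw variance. The gain from height will also be smaller than the gain from limb length to the extent that height is an imperfect proxy for it.

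Stating the model matters more than choosing the scale. The documents do not support a claim of systematic bias, or a claim that expressing reach as a percentage of limb length would by itself deliver the gains shown.

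**What to change.** In the Data analysis section, state that the week 3 and week 6 models for each Y Balance direction will include, as covariates, the participant's pre-tape day-1 reach in that direction and height. Specifying the pre-tape value matters because the tests are repeated after taping on the same day.

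Optionally, record stance-limb length once on day 1 and use it as the covariate in place of height. Percent of limb length can then be reported as a descriptive scale.

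The core change needs no new data and costs two degrees of freedom, one per covariate. The optional part adds one tape reading per participant.

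### Tape tension rises every week, but no record of skin tolerance, early loss or days worn is described, and the wear limit has no usable number

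*Combined protocol and SAP*

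**What the plan says.** All of this is in the Procedures text of the combined protocol and SAP, in the paragraphs on bandage application and care and in the items for the two groups.

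- **Experimental group:** "Each week the tension of the tapes will be increased, increasing 5% of tension per week in relation to the initial length". No condition other than the passing week is attached.
- **Control group:** "The applications will not suffer an increase in the tension of the tapes, they will only be placed on the application site".
- **Frequency, same wording in both groups:** "the application of the bandage will be carried out weekly, for five weeks, in the individuals allocated to this group".
- **Care instructions:** participants are told "do not remove and replace the bandage" and to "keep the application up to the room day after placed".
- **Assessments:** "Initial assessment will be carried out on the first day, reevaluations in the third week and in the sixth week after the initial assessment".

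The entry form covers demographics, activity and injury history. The outcome measures are two questionnaires, the force platform, the Y Balance Test and the side hop test. Neither list, nor the description of the applications, includes skin state, discomfort, loss of tape or time worn.

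**The concern.** Tension is the only planned difference between the groups, and the exposure of interest is tension delivered over time. To interpret the result one needs to know how long each tape stayed on and how it was tolerated. The plan describes collecting neither, although every participant is due for re-taping each week. The intended wear time is also unclear, because the sentence that should give it contains no number.

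Two things are at stake. If the week-6 comparison shows no difference, nobody could say whether progressive tension had no effect or the tape had not been worn. And the trial could not report by group whether progressive tension was tolerated, which a reader would expect from a study of a protocol that tightens weekly. These data cannot be recovered reliably once the trial is over.

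**Working it through.** The plan gives no figure for exposure, sample size or power, so there is nothing to reproduce. The check is arithmetic on the schedule, followed by a comparison of what is done with what is recorded.

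**Inputs from the document:** five applications, 7 days apart; a step of 5 per week in the experimental group; reevaluations in the third and sixth weeks.

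**Not given:** the starting tension, the wear limit in days, and whether the tape applied on day 1 is the first of the five.

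**1. Tension.** Application *i* has tension T₁ + 5 × (*i* − 1). For the fifth, T₅ − T₁ = 5 × 4 = 20 percentage points. The difference does not depend on the start: from 0% the path is 0, 5, 10, 15, 20; from 5% it is 5, 10, 15, 20, 25. In the control group the difference is 0.

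**2. Wear.** With *w* days per application, total wear is 5 × *w*, and 7 − *w* tape-free days precede the next application. As *w* is unreadable, I assume 1 to 7:

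- *w* = 1: 5 × 1 = 5 days in total, 7 − 1 = 6 tape-free days between applications.
- *w* = 7: 5 × 7 = 35 days in total, 7 − 7 = 0 tape-free days.

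If the day-1 tape is additional to the five, there are six tapes and the range becomes 6 × 1 = 6 to 6 × 7 = 42 days.

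**3. Calendar.** Take the initial assessment as day 0. If the five applications start on day *s*, the fifth falls on day *s* + 28, and the gap to a final visit on day *R* is *R* − (*s* + 28). The sixth week may mean its start (day 35), its end (day 41) or six full weeks (day 42).

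| Start of the five applications | Fifth application | Gap, R = 35 | Gap, R = 41 | Gap, R = 42 |
|---|---|---|---|---|
| Day 0 (s = 0) | day 28 | 7 | 13 | 14 |
| One week later (s = 7) | day 35 | 0 | 6 | 7 |

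The gap after the fifth application is therefore 0 to 14 days, against 7 between successive applications.

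**4. Done versus recorded.** The text covers hair removal, skin cleaning, tape technique, drying with a towel and what to do about lifting ends. It thus foresees that tape may start to come off, but describes no record of whether or when it does.

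**The case against.** The strongest reply is that this is a very short text and silence proves little. Participants sign a consent form that is not part of the text reviewed here, and advice on reactions may be given there. That stands in part: the document shows that nothing is described, not that nothing will be done. It does not supply a data item that could be analysed by group.

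A reader might infer that a participant with a reaction would be re-taped more tightly without anyone looking at the skin. The document does not support this. A qualified professional applies the tape, and the site preparation is described as "The application area will be previously free of hair (performing trichotomy) and asepsis with 70% alcohol". If that is repeated at each application, which the text does not say outright, someone handles the skin every week. The gap is in recording.

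It can also be said that a fixed weekly increase is the intervention under test and that the plan does not contradict itself on it. That is right, and the escalation itself is not criticised here.

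The wear sentence looks like a translation slip for an ordinal day, which the sponsor can settle with one word. If the limit is well short of a week, the upper end of the wear range falls away. The need to know the days actually worn remains.

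Finally, missing wear data do not bias the randomised comparison of assigned protocols. That is also correct; they limit how the result can be explained.

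**Conclusion.** The point holds as a gap in data collection together with an unusable wear instruction. Planned tension at the fifth application is 20 percentage points above the first in one group and unchanged in the other, while wear and tolerance are not described as recorded in either. The 5 to 35 day range rests entirely on the assumed 1 to 7 days per application. It shows how little the text fixes and is not an estimate of actual wear.

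Three stronger readings are tempting and not supported:

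- **That participants are forbidden to take the tape off.** The instruction is "do not remove and replace the bandage", which most naturally bars peeling and re-sticking, and the same sentence goes on to set an end to wear. What is missing is any statement of what a participant should do if the tape is not tolerated.
- **That the tightest tape is followed by the longest interval without contact.** This is so only if the five applications start on day 0 and the final visit falls after day 35. On the other readings the last gap equals 7 days or is shorter.
- **That intolerance or early loss will differ by group.** This is plausible because tension differs, but the document gives no figure for it. The point is that the plan as described could not detect a difference if one arose.

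This is an inexpensive improvement to make before data collection, not a defect that invalidates the trial.

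**What to change.** 1. At each existing weekly visit, before re-taping and in both groups, complete one short form: skin state at the site, pain or numbness, whether the tape came off or was removed early and why, and days worn. Complete the same form for the fifth application at the sixth-week reevaluation. Its answers may rely on recall over as many as 14 days, depending on the calendar, so the application date and the visit date should both be recorded.
2. Add to the Data analysis paragraph that these items will be summarised by group.
3. The sponsor should correct the wear-limit sentence and reconcile it with the care instruction, the weekly escalation and the visit calendar. This includes stating whether the day-1 application is the first of the five and which day the sixth-week visit means.

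No tension, wear time or stopping rule is proposed; those are for the sponsor.

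The cost is a few minutes of recording per visit and some corrected wording. No extra visit is needed, and the intervention and the primary comparison are unchanged.

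### Each outcome is tested separately at 5%, with no primary outcome, deciding visit, specific between-group effect or multiplicity control named in the documents provided

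*Combined protocol and SAP*

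**What the plan says.** The Data analysis section of the combined protocol and SAP has three elements. It opens with a distribution check: "The normal distribution of the sample data will be analyzed using the Shapiro Wilk test". It then gives the comparison of tape without tension against tape with tension: "If normality is established, an analysis of variance of the factors will be used for each dependent variable to compare the groups". It closes with the software and the threshold: "All statistical analyzes will be performed in the SPSS statistical program (version 20.0) with the adopted significance of 5" per cent.

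The variables have to be inferred from Procedures:

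- **Force platform:** "evaluations of static postural control will be carried out through the force platform", in three runs. No parameter is named, and the text does not say how the runs are combined.
- **Y Balance Test:** three directions. "Each of the directions is tested three times and the 3 repetitions are averaged". No composite score is mentioned.
- **Side hop test:** ten jumps done as fast as possible, so presumably a time.

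The tests are done on day 1 before taping and again once the tape is on ("After applying the bandage, the volunteers will again perform the tests mentioned above"). They are repeated at "reevaluations in the third week and in the sixth week after the initial assessment".

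Neither Procedures nor Data analysis labels an outcome as primary, names a deciding visit, lists the factors of the analysis of variance, or mentions a hierarchy or an adjustment for several tests.

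**The concern.** The trial asks whether tape applied with tension differs from tape applied without it. The plan states that comparison but not which result answers it. Three choices stay open until after the data are seen: the variable, the visit, and the form of the group comparison (group effect averaged over visits, group-by-time effect, or group difference at one visit).

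The 5% applies to each test. If any one significant result may be presented as the finding, the chance of a positive report when tension makes no difference is above 5%. A reader of the eventual paper could not tell from this plan whether the highlighted outcome was the intended one. A choice made after the results are known cannot later be made prespecified.

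**Working it through.** **What can be reproduced.** The only design figure in the documents is the 5% level. One test at 0.05 has a type I error of 0.05. No sample size, power, effect size or number of tests is given, so there is nothing else to reproduce.

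**Inputs.**

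- Level per test: 0.05, from Data analysis.
- Number of variables, k: not stated. From Procedures, 1 platform measure + 3 Y Balance directions + 1 side hop measure = 5, with a single platform parameter assumed. Merging the three directions gives 1 + 1 + 1 = 3. The analysis sentence speaks of two tasks although three tests are described; one variable per task would give k = 2. The two questionnaires are left out because they are described only at entry.
- Tests per variable: one group test (assumed).
- Correlation between test statistics, ρ: not in the documents; assumed common to all pairs, from 0 to 0.9.

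**Independent tests, no true effect.** P(at least one p < 0.05) = 1 − 0.95^k.

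- k = 5: 1 − 0.7738 = 0.2262
- k = 3: 1 − 0.8574 = 0.1426
- k = 2: 1 − 0.9025 = 0.0975

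**Correlated tests.** For two-sided normal statistics with common correlation ρ and critical value c = 1.960,

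P = 1 − ∫ [Φ((c − √ρ·x)/√(1−ρ)) − Φ((−c − √ρ·x)/√(1−ρ))]^k φ(x) dx,

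evaluated numerically:

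| Variables | ρ = 0 | 0.3 | 0.5 | 0.8 | 0.9 |
|---|---|---|---|---|---|
| 5 | 22.6% | 20.9% | 18.3% | 12.7% | 10.2% |
| 3 | 14.3% | 13.6% | 12.5% | 9.8% | 8.4% |
| 2 | 9.8% | 9.5% | 9.1% | 7.8% | 7.0% |

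Every cell exceeds 5%, including two variables correlated at 0.9.

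**After the fix.** One named variable, visit and effect, tested once at 5%, gives a type I error of 5.0% for the primary claim, whatever the correlation with the other variables.

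**The case against.** The strongest reply is that the plan makes no claim of family-wise control and no explicit confirmatory claim, so none of its stated numbers is wrong. That is correct. What it leaves untouched is the missing decision rule, which would be a gap even if the outcomes were very highly correlated.

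Second, the comparison of interest is stated: the analysis of variance is there to compare the two tape groups. A reader might infer that the plan leaves even this open, so that a change over time alone could count as success. The text does not support that. The gap is narrower: which form of the group comparison decides.

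Third, the error rates depend on assumed counts and correlations. This stands, and they should be read as illustration. A reader might infer that 22.6% is the error rate of this trial, or go further: reading both a group and a group-by-time effect for five independent variables gives 1 − 0.95^10 = 40.1%, and five variables at three occasions after taping gives 1 − 0.95^15 = 53.7%. The documents support neither as a property of the plan. They do not list the variables, and they do not say that either of two effects, or any of three visits, would count as success.

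Fourth, several nearby gaps might seem to make the problem worse: whether the week-6 tests are done with tape ("the application of the bandage will be carried out weekly, for five weeks" suggests week 6 follows the last application, but this is not stated), the lack of any analysis if normality fails, and the mismatch between two tasks and three tests. These are separate clarifications and add nothing to the weight of this point.

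Finally, a primary outcome may be named in a source not provided here. That cannot be checked, so the point is confined to these documents.

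**Conclusion.** The concern holds in this limited form. As written, the plan tests every outcome variable at 5% and does not fix the outcome, the visit or the form of the group comparison that decides the trial. Under one group test per variable and no true effect, the illustrative chance of at least one false positive runs from 7.0% (two variables, correlation 0.9) to 22.6% (five independent variables). The exact value cannot be known, because the number of variables and their correlation are not in the documents; that it exceeds 5% does not depend on which of these readings is taken.

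This does not show that analysis of variance is the wrong method or that the stated 5% is wrong. It needs correcting before outcome data are examined, because it affects the trial's only comparison.

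**What to change.** Before outcome data are seen:

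1. Name one primary outcome. If the force platform is chosen, give the exact parameter and how the three runs are combined.
2. Name one visit and one between-group effect, tested at two-sided 5%. One example, the choice being the investigator's, is the week-6 difference between groups adjusted for the day-1 pre-tape value, which is already collected. If a group-by-time effect is preferred, name it and the occasions it covers.
3. Label all other variables, visits and effects secondary or exploratory, and state that none of them can by itself support a positive conclusion.

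Holm testing of the secondary outcomes after a significant primary is optional, and statisticians differ on whether it is needed. If used with four secondaries, its first step is 0.05/4 = 0.0125; a comparison with a hypothetical 80% power at 0.05 would have about 62% there.

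**Cost.** No new measurements or visits. Results on the other variables no longer count as confirmatory, and the example model replaces the planned analysis of variance. Because no sample size or power is given, the power of the chosen primary test cannot be checked from these documents.
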